## 5.7 Product Accountability

In accordance with regulatory requirements, study sites must document the amount of belumosudil received from and returned to the Sponsor, the amounts of belumosudil dispensed to study subjects, and the amount returned by study subjects. Product accountability records must be maintained throughout the course of the study.

#### 5.8 Concomitant Medications and Procedures

All concomitant medications including dietary/herbal/over the counter supplements taken during the study and relevant procedures will be recorded. Initiation of new systemic cGVHD therapy will be considered a new line of treatment and a belumosudil treatment failure.

#### 5.8.1 Corticosteroids

Corticosteroid dose data will be collected throughout the study. Corticosteroids may be tapered at the discretion of the Investigator.

Transient increases in corticosteroid dosing (not exceeding 1 mg/kg/day prednisone equivalent, see Appendix K: Prednisone Dose Equivalents) are permitted for the treatment of cGVHD flare, but the dose must be reduced within 6 weeks. If the dose remains elevated for more than 6 weeks, this will be considered a belumosudil treatment failure.

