### 6.3 Efficacy Endpoints

The efficacy endpoints of this study will be:

- Duration of Response (DOR)
- Change in LSS (Appendix D: Lee cGVHD Symptom Score)

- Time to Next Treatment (TTNT): defined as the time from the first dose of belumosudil to the start of additional systemic cGVHD therapy
- FFS: defined as the absence of cGVHD treatment change, non-relapse mortality, and recurrent malignancy
- Overall Survival (OS): defined as the time from first dose of belumosudil to the date of death due to any cause
- Percentage of subjects who have a best response of CR and percentage of subjects who have a best response of PR
- Response by individual organ
- Change in corticosteroid dose: the change in prednisone equivalent dose of corticosteroids (mg/kg/day) during the study
- Change in cGVHD Global Severity Rating using the Clinician-reported Global cGVHD Activity Assessment (Appendix B: Clinician-reported Global cGVHD Activity Assessment)

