3.7.2.3 Time to Next Treatment (TTNT)

The TTNT will be measured as the time from first treatment to the time of new systemic cGVHD treatment (which will be defined by clinical team review), censored by last response assessment or long term follow up assessment, whichever is the latest and available. TTNT will be analyzed

Kadmon Corporation

Page 17 of 26

by the Kaplan-Meier survival method as well as the landmark analysis at 6, 12, 18, and 24 months.

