3.7.2.4 Failure-free-survival (FFS)

FFS is defined as the absence of new cGVHD systemic therapy, non-relapse mortality and recurrent malignancy (i.e., underlying disease) and is censored by last response assessment or long term follow up assessment, whichever is the latest and available. Kaplan-Meier plots, descriptive statistics of FFS and landmark FFS at 6, 12, 18, 24, 30 and 36 months will be provided. In addition, analyses for the three components of FFS will also be provided.

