3.7.2.8 Change in corticosteroid dose

Corticosteroid doses will be presented as mg/kg/day prednisone equivalent dose. Any corticosteroid dose increases to ≥ 0.9 mg/kg PE during the study is counted as new systemic cGVHD therapy.

Descriptive statistics for the Full Analysis Set will be provided for:

- Both prednisone equivalent dose and change-from-baseline values (summary score and domain scores) will be summarized as continuous variables by visit
- Change and % change from baseline to the greatest corticosteroid dose reduction at any post-baseline visit
- Number and % of subjects who reduced systemic corticosteroid dose at any postbaseline visit
- Number and % of subjects who ever discontinued systemic corticosteroid usage at any post-baseline visit

If subjects are not using prednisone as the systemic corticosteroid, then the prednisone dose equivalent will be determined according to following conversion ratios2:

1 mg prednisone is equivalent to:

- 4mg Hydrocortisone
- 0.8mg Methylprednisolone
- 0.15mg Dexamethasone
- 1mg Prednisolone

Kadmon Corporation

Page 19 of 26

0.8mg Triamcinolone

3.7.2.9 Change in cGVHD Global Severity Rating based on the Clinician-reported Global cGVHD Activity Assessment

The Clinician-reported global cGVHD Activity Assessment is a 0-10 point numeric rating scale with a score of 0 indicating "cGVHD symptoms not at all severe" and a score of 10 being "Most severe cGVHD symptoms possible". The activities are assessed on at baseline and then every 3 months after.

Change from baseline in cGVHD severity based on the Clinician-reported global cGVHD Activity Assessment will be summarized as a categorical endpoint at all scheduled assessment visits.

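### The protocol defines steroid-related failure by duration and the SAP by dose, so the same steroid course can be a failure in one document and not in the other, in both directions

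*Protocol*

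**What the plan says.** **Protocol.** Section 5.8.1 allows short steroid increases for a flare: "Transient increases in corticosteroid dosing (not exceeding 1 mg/kg/day prednisone equivalent, see Appendix K: Prednisone Dose Equivalents) are permitted". The dose must come down within 6 weeks. Otherwise: "If the dose remains elevated for more than 6 weeks, this will be considered a belumosudil treatment failure". No minimum dose is attached to that sentence. Section 5.8 uses the same failure label for a different trigger: "Initiation of new systemic cGVHD therapy will be considered a new line of treatment and a belumosudil treatment failure". In section 6.3 the TTNT event is "defined as the time from the first dose of belumosudil to the start of additional systemic cGVHD therapy". FFS is worded more broadly: "FFS: defined as the absence of cGVHD treatment change, non-relapse mortality, and recurrent malignancy".

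**SAP.** Section 3.7.2.8 has one steroid trigger: "Any corticosteroid dose increases to ≥ 0.9 mg/kg PE during the study is counted as new systemic cGVHD therapy". It sets no duration, and no other SAP section carries the 6-week rule. For TTNT (section 3.7.2.3) the event is "new systemic cGVHD treatment (which will be defined by clinical team review". For FFS (section 3.7.2.4): "FFS is defined as the absence of new cGVHD systemic therapy, non-relapse mortality and recurrent malignancy". In Table 2 of section 3.7.2.1, new therapy for cGVHD is an event in all five DOR definitions. Four of them also end at a response-based event. The tertiary definition ends only at new systemic therapy or death.

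**The concern.** The protocol attaches its treatment-failure label to two things: new systemic therapy, and a steroid increase that is not brought down in time. The SAP carries the first into its events. It replaces the second with a dose threshold and does not explain the change. An analyst who follows the SAP as written will therefore classify some subjects against the protocol's own failure rule.

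Long-term efficacy is a stated objective, and FFS, TTNT and DOR are the time-to-event measures that describe it. If prolonged added steroid at a moderate dose leaves a subject failure-free, while a brief permitted increase at a higher dose counts as new therapy, a reader of the results cannot tell which notion of failure the curves represent.

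**Working it through.** The plan states no rate, event count or power figure on this point (SAP 3.1.2 has no power calculation), so there is nothing to reproduce. The check has three parts.

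**1. Classify courses under each rule.** Inputs: the 1 mg/kg/day ceiling and the 6-week limit (Protocol 5.8.1), and the 0.9 mg/kg threshold (SAP 3.7.2.8).

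| Course (example) | Protocol 5.8.1 | SAP 3.7.2.8 | SAP time relative to the protocol rule |
|---|---|---|---|
| Below 0.9 mg/kg, more than 6 weeks (0.5 for 8 weeks) | Failure | No event | Longer |
| 0.9–1.0 mg/kg, 6 weeks or less (0.95 for 4 weeks) | Permitted | Event | Shorter |
| 0.9–1.0 mg/kg, more than 6 weeks (0.95 for 8 weeks) | Failure, met only after week 6 | Event at the increase | Shorter (earlier date) |
| Below 0.9 mg/kg, 6 weeks or less (0.5 for 4 weeks) | Permitted | No event | Same |

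A short rise above 1 mg/kg (for example 1.2 for 4 weeks) falls outside the protocol's allowance. The protocol does not label it a failure; the SAP counts it as an event.

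**2. Trace each endpoint.**

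- *FFS.* The protocol's treatment-change wording could cover a sustained steroid increase. The SAP narrows it to new systemic therapy and has no review step for FFS. Exposed.
- *Tertiary DOR.* There is no response-based event to fall back on. Exposed.
- *TTNT.* Exposed unless the clinical team review, for which no criteria are written, picks up the case.
- *Primary, secondary, quaternary and FDA DOR.* A flare recorded at a visit as deterioration, lack of response or organ-level progression ends the response whatever the steroid dose. Exposure is smaller but not nil: visits are 3 months apart and response is judged against parent-study Cycle 1 Day 1, so a flare controlled by added steroid may still be rated a response at the next visit.

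**3. Illustrate direction and size.** All rates here are assumptions, because the documents give none. Let S be the landmark probability of being free of all other events, a the probability of a sustained rise below 0.9 mg/kg, and b the probability of a rise to 0.9–1.0 mg/kg lasting 6 weeks or less, taken as independent. Then:

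- SAP landmark = S(1 − b)
- Protocol-rule landmark = S(1 − a)
- Difference (SAP minus protocol rule) = S(a − b)

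| S | a | b | SAP | Protocol rule | Difference |
|---|---|---|---|---|---|
| 0.6 | 0.10 | 0 | 60.0% | 54.0% | +6.0 points |
| 0.6 | 0.05 | 0.05 | 57.0% | 57.0% | 0 |
| 0.6 | 0.05 | 0.10 | 54.0% | 57.0% | −3.0 points |

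With S from 0.4 to 0.8 and a and b each from 0 to 0.10, the extremes are ±0.8 × 0.10 = ±8 points. For scale, one subject of about 70 (Protocol 4.1) is 1/70 = 1.4 points.

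**The case against.** The strongest reply is that the protocol never makes a section 5.8.1 failure an endpoint event. Its TTNT event is the start of additional systemic therapy, and a longer course of a steroid already in use is not plainly that. Section 5.8 calls new systemic therapy both a new line and a failure; section 5.8.1 says only failure. On TTNT the SAP can therefore be read as following the protocol, with a clinical review as backstop. Most DOR definitions also have their own response-based endings, and the study is descriptive, with no formal hypothesis (Protocol 9.1).

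Much of this stands. It limits the point for TTNT and for four of the five DOR definitions. It does not remove it for FFS, where the protocol wording is broader than the SAP's, or for tertiary DOR. Nor does it explain why the SAP makes steroid escalation an event on a criterion different from the protocol's.

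Timing also limits TTNT. Its landmarks run from 6 to 24 months after the first belumosudil dose. The KD025-213 cutoff of 19 February 2020 was 6 months after the last subject's first visit (Protocol 1.4.2), so 24 months from first dose was reached by about August 2021. If entry to this study was near the Amendment 1 date of 08 September 2021 (an assumption), the main-cohort subjects had already passed the last TTNT landmark. Whether the parent protocols had a 6-week rule is not in these documents. The FFS landmarks run to 36 months and are less protected.

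**Conclusion.** The conflict is real: one document defines steroid-related failure by duration and the other by dose, and they disagree in both directions. FFS and tertiary DOR are most affected, TTNT conditionally, and the other DOR definitions less.

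A reader might infer that the SAP overstates FFS, TTNT and every DOR. The documents do not support that. The sustained low-dose rises that the SAP misses lengthen its times, but the short high-dose rises that it adds, and its earlier dating of long high-dose courses, shorten them. There is equally no basis for assuming that these cancel, since they affect different subjects.

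A reader might also turn an assumed 3% to 10% of subjects into a bias of 3 to 10 points. That only restates the assumption, and it ignores subjects who fail for other reasons as well as the opposite mismatch. What can be said is that each reclassified subject is worth about 1.4 points of about 70. The ±8-point range is illustrative and rests on assumed, independent rates. The point deserves correction before analysis, but it invalidates no test, because none is planned.

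**What to change.** Reconcile Protocol 5.8.1 and 6.3 with SAP 3.7.2.3, 3.7.2.4 and 3.7.2.8. Which steroid rule is clinically right is for the sponsor to settle. The statistical requirement is consistency:

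- State in SAP 3.7.2.8 one steroid-failure definition and one event date, used in FFS, TTNT and DOR. Say explicitly how an increase lasting more than 6 weeks is counted.
- Write down the criteria that the clinical team review applies for TTNT, and say whether the review also governs FFS and DOR.
- Report FFS, TTNT and tertiary DOR under the other definition as a sensitivity analysis.

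The cost is SAP wording and a derivation from steroid doses already recorded on treatment. Reported rates may come out slightly less favourable. One limit should be stated with the results: steroid dose is collected only until 28 days after the last dose (Protocol Appendix A). Long-term follow-up contacts record survival, new systemic therapy and relapse but not steroid dose (Protocol 6.2.5). The derivation therefore cannot cover later follow-up, or subjects who entered already in long-term follow-up, and ascertainment will differ on and off treatment.

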### 5.8.2 Systemic cGVHD Therapies

Subjects may be receiving the standard of care systemic cGVHD therapies such as CNIs (tacrolimus, cyclosporine), sirolimus, mycophenolate mofetil, methotrexate, rituximab, or ECP. Changes in doses of drugs to maintain therapeutic levels are not considered as a change in dose/schedule.

# 5.8.3 Topical / Organ Specific Therapies for cGVHD

Use of topical/organ specific therapies for cGVHD is permitted but must be documented.

#### 5.8.4 CYP 3A4 Inducers

Use of strong CYP3A4 inducers decreases belumosudil exposure (Appendix H: Drugs that Induce CYP3A4).

### 5.8.5 Drugs Prolonging the QTc Interval

Drugs that prolong QT/QTc should be used with caution (Appendix J: Drugs That Prolong QTc).

#### 5.8.6 Prohibited Concomitant Medications

Treatment with investigational systemic immunosuppressant drugs for cGVHD (including ruxolitinib) is prohibited.

#### 5.9 Treatment of Overdose

Doses of belumosudil considered to represent an overdose have not been defined. In clinical studies of belumosudil in healthy volunteers, repeat dosing of 500 mg BID for 28 days was generally well-tolerated. There are no known antidotes to belumosudil; no specific treatment is recommended in the event of a suspected overdose. The treating Investigator should employ clinical judgment in managing subjects with suspected overdose. Overdose should be reported as an AE (Section 7.2) regardless of whether there are any other associated AEs.

### 5.10 Dose Modification Guidelines

Any clinically significant toxicity will necessitate consideration of either a pause or cessation of therapy. Guidelines for management of treatment-emergent toxicities in subjects receiving belumosudil are outlined in Table 5. When dose reduction is necessary, the dose should be decreased as shown in Table 6.

Table 5. Guidelines for the Management of TEAEs with Belumosudil Treatment

Toxicity	Recommended Action		
Grade 4 organ toxicities considered at least possibly related to belumosudil	Discontinue belumosudil		
Grade ≥ 3 LFTs (AST, ALT or total bilirubin) regardless of attribution to belumosudil	
 
Hold belumosudil dosing until resolution to Grade 1 or below levels
 
Consider resuming belumosudil. If resuming, then resume at 1 dose decrement
 
If toxicity recurs, discontinue belumosudil
 
		
Other Grade ≥3 clinically significant toxicities considered at least possibly related to belumosudil	Hold belumosudil dosing until toxicity has resolved to Grade 1 or below then consider resuming belumosudil. If resuming, then resume at 1 dose decrement     If toxicity recurs, hold dose as above then consider resuming belumosudil at one dose decrement		

ALT = alanine aminotransferase; AST = aspartate aminotransferase; eCRF = electronic case report form; LFT = liver function test; TEAE = treatment-emergent adverse event

Dose interruption for up to 14 days for toxicity management is permitted. Subjects requiring pauses of more than 14 days will be discontinued from the study unless approved by the medical monitor.

Table 6. Belumosudil Dose Decrements

Belumosudil Dose	Dose Reduction	
400 mg QD	200 mg QD	
200 mg BID	200 mg QD	
200 mg QD	200 mg QOD	

BID = twice daily; QD = once daily; QOD = once every other day

If the reduced dose of belumosudil is tolerated for 1 month, the dose may be escalated to the previous dose.

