#### 7 SAFETY

#### 7.1 Safety Parameters

The Common Terminology Criteria for Adverse Events version 4.03 (CTCAE v4.03) will be used for classifying laboratory results and grading AEs. Subjects will be monitored throughout the treatment and follow-up period for occurrence of AEs (acute, delayed, and/or cumulative) as well as for changes in clinical status, vital sign measurements, and laboratory data. Safety parameters to be measured/assessed include vital sign measurements; PE; hematology and serum chemistry results; and ECG recordings.

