### 7.4 Other Safety Considerations

#### 7.4.1 Laboratory Data

All laboratory data obtained during the course of the study should be reviewed. Any abnormal value that leads to a change in subject management (e.g., dose reduction or delay, requirement for additional medication or monitoring) or is considered to be of clinical significance by the

Investigator should be reported as an AE and/or SAE as appropriate, unless this value is consistent with the subject's present disease state or is consistent with values obtained before entry into the study.

Laboratory results will be classified using the CTCAE v4.03.

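### Protocol Table 5 gives two different instructions for a Grade 4 AST, ALT or bilirubin rise judged at least possibly related to belumosudil

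*Protocol*

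**What the plan says.** Protocol section 5.10, Table 5, sets out three triggers, each with a recommended action.

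- **Row 1.** Trigger: "Grade 4 organ toxicities considered at least possibly related to belumosudil". Action: "Discontinue belumosudil". There is no provision for restarting.
- **Row 2.** Trigger: "Grade ≥ 3 LFTs (AST, ALT or total bilirubin) regardless of attribution to belumosudil". Action: "Hold belumosudil dosing until resolution to Grade 1 or below levels", followed by "Consider resuming belumosudil. If resuming, then resume at 1 dose decrement". Permanent discontinuation comes only if the toxicity recurs.
- **Row 3.** Trigger: "Other Grade ≥3 clinically significant toxicities considered at least possibly related to belumosudil". Action: a hold, then possible resumption at one decrement, with the same approach on recurrence.

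Text around the table adds two rules. A pause for toxicity of more than 14 days ends the subject's participation unless the medical monitor approves otherwise. A subject who tolerates a reduced dose for one month may return to the previous dose.

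On grading, Protocol section 7.1 states: "The Common Terminology Criteria for Adverse Events version 4.03 (CTCAE v4.03) will be used for classifying laboratory results and grading AEs". Protocol section 7.4.1 makes reportable as an adverse event "Any abnormal value that leads to a change in subject management", except where the value fits the subject's present disease state or values obtained before study entry.

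**The concern.** Row 2 has no upper grade limit and applies whatever the attribution. Row 1 has no exception for liver tests. A Grade 4 liver-test rise attributed at least possibly to the drug therefore appears to fall under both, and the two actions differ on a point that matters: whether the subject may receive belumosudil again.

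Two things are at stake. The first is subject safety, because the protocol does not give sites one answer on re-exposure after a serious drug-related liver event. The second is how the safety results are read. Long-term safety is part of the study objective (Protocol section 2). SAP section 3.3 summarises treatment discontinuations with their primary reason, and SAP section 3.8.1 tabulates separately the events leading to dose modification and those leading to study drug discontinuation. The row that a site follows can decide which of these tables the event enters.

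**Working it through.** The documents state no figure to reproduce, so the first check is logical. Each combination of grade, type of event and attribution is tested against the three triggers.

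| Event | Row 1 | Row 2 | Row 3 | Result |
|---|---|---|---|---|
| Grade 4 AST, ALT or bilirubin, related | yes | yes | no | **two different actions** |
| Grade 4 AST, ALT or bilirubin, unrelated | no | yes | no | one action |
| Grade 3 AST, ALT or bilirubin, any attribution | no | yes | no | one action |
| Grade 4 other organ toxicity, related | yes | no | no | one action |
| Grade 4 toxicity that is not an organ toxicity, clinically significant, related | no | no | yes | one action |
| Grade 3 toxicity other than liver tests, clinically significant, related | no | no | yes | one action |

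Here *related* means at least possibly related. Exactly one combination receives two actions.

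**Is a liver-test rise an organ toxicity?** The first line of the table needs a yes. The protocol does not define the term. Three points favour yes. Laboratory results are graded on the same CTCAE scale as adverse events (section 7.1). A value that changes management is normally an adverse event (section 7.4.1). Protocol Appendix C and SAP Appendix A treat the liver as an organ assessed by ALT, alkaline phosphatase and total bilirubin. The appendices concern efficacy and do not name AST, so they support this reading without settling it.

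**Does another section set precedence?** No. Protocol section 4.8 lists an adverse event requiring permanent discontinuation but does not say which events those are. Section 4.6 refers to unacceptable toxicity without defining it. Section 8 states that there are no stopping rules. The 14-day rule in section 5.10 concerns the length of a pause, not the choice of row.

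**How often could it arise?** The documents give no count of related Grade 4 AST, ALT or bilirubin events. The nearest figures are for Grade 3 or higher, so they only bound the answer from above.

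- KD025-208 (Protocol Table 2): related Grade ≥ 3 ALT increased 2/54 and AST increased 2/54. The two counts cannot be added. Cohort 1 had only one subject with any related Grade ≥ 3 event, yet shows one ALT and one AST case, so these are the same person. Cohort 2 shows one of each, which is one or two people. The total is 2 or 3 subjects.
- KD025-213 (Protocol Table 4): the list of related Grade ≥ 3 terms above 1% contains no AST, ALT or bilirubin term. Since 1% of 132 is 1.32, a term with 2 subjects would have been listed, so each occurred in at most 1/132.
- Pooled, per enzyme: between (2 + 0)/(54 + 132) = 2/186 = 1.1% and (2 + 1)/186 = 3/186 = 1.6%.
- Applied to the planned enrolment of about 70: 70 × 2/186 = 0.75 to 70 × 3/186 = 1.13 subjects per enzyme at Grade 3 or higher.

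The last line is an illustration. It assumes that all 70 are dosed and that parent-study rates carry over. Subjects entering in long-term follow-up receive only follow-up contacts (Protocol sections 6.2.2 and 6.2.5), so the number dosed is smaller and is not stated. The longer treatment here could act in the other direction. Grade 4 events are a subset of these counts, of unknown size.

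**The case against.** Several arguments can be made for leaving the table alone.

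*The row naming the liver tests governs.* This is plausible, since row 2 names three analytes while row 1 uses a general term. But row 1 is the narrower row on grade and on attribution. The table signals a residual category in row 3 and gives no such signal between rows 1 and 2, so the reader has to supply the rule.

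*The rows are compatible.* This is partly right. Both stop dosing at once, and row 2 asks only that resumption be considered. A site that withholds the drug and never restarts satisfies both. A reader might infer that sites would manage the acute event in opposite ways; the text does not support that. The difference is confined to whether later re-exposure is allowed. It is still a real difference, because under row 2 the subject may restart and, after a tolerated month, return to the previous dose.

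*These are guidelines, and investigators may stop treatment anyway.* The table is headed as guidance with recommended actions, and investigator decision is a listed reason for stopping (Protocol sections 4.6 and 4.8), so some variation between sites would exist regardless. That softens the consequence. It does not help an investigator who consults the table and finds two answers.

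Two further inferences should be resisted. A reader might think that row 3 also contradicts row 1, since it too includes Grade 4. It opens with *Other*, which removes events already covered above; only the undefined edge of organ toxicity is left unclear. A reader might also take the parent-study Grade 4 totals, 7/54 and 5/132, as the size of the problem. Those are maximum-severity counts for all organs and all causes and say nothing about related liver-test events.

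**Conclusion.** The inconsistency is real and limited to one type of event: a Grade 4 AST, ALT or total bilirubin elevation judged at least possibly related. For that event, row 1 rules out re-exposure and row 2 permits it, with nothing in the documents to choose between them. The finding assumes that a Grade 4 liver-test rise counts as an organ toxicity, which is the natural reading but is not stated.

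Few if any cases are expected, and the documents do not allow a firmer number. The effect on the analysis is correspondingly small: one reclassified subject among about 70 is 1/70 = 1.4 percentage points overall, and more within a single dose group. The study has no formal hypothesis (Protocol section 9.1), so no test is affected. The reason to act is that a safety instruction for a serious event conflicts with itself, and correcting it costs very little.

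**What to change.** Amend Protocol section 5.10, Table 5, so that a Grade 4, at least possibly related AST, ALT or total bilirubin event maps to one stated action. This can be done with an explicit exception in one of the two rows or with a sentence giving precedence. In the same edit, say whether liver-test elevations count as organ toxicities, which also clarifies the border with row 3. Which action applies is for the sponsor's clinical team to decide; this review takes no position.

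The cost is a wording amendment, with no added procedures or subjects. The SAP needs no change, since its summaries of discontinuation and dose modification already accommodate either outcome.
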